# 25.2.2. Part 2 Olaparib: Dose Modifications

Every effort should be made to administer olaparib at the planned dose and schedule. Any toxicity observed during the course of the trial treatment should be managed by interruption of olaparib, as deemed appropriate by the Investigator. Patients experiencing toxicities related to the olaparib may have their dose modified as outlined in this section. Further guidance on specific toxicities requiring dose modifications are described in Sections 25.2.2.

Any dose reductions should be applied to subsequent cycles unless a further dose reduction is required. Once a reduction is made the patient should not increase back to a higher dose level.

Table. Olaparib dose reductions guidelines

Dose Level	Olaparib
Starting dose	300mg BD Days 1-28
First dose reduction	
For haematological toxicity	250mg BD Days 1-28
For non-haematological toxicity	250mg BD Days 1-28
Second dose reduction	200mg BD Days 1-28
Third dose reduction	Discontinue trial treatment

IRAS Project Number: 249774

The haematological criteria for initiation of a treatment cycle are blood counts on Day 1 of any cycle (within 72 hours pre-treatment):

- ANC  $\geq$ 1500/mm^3 ( $\geq$ 1.5 x 10^9/L)
- Platelet count ≥75,000/mm³ (≥75x 10^9/L)
- Haemoglobin (Hb) ≥8g/dL (≥80g/L) (with the exception of Cycle 1 where Hb must be >10g/dL (100g/L)).

# 25.2.3. Part 2 Olaparib: Specific Toxicities Requiring Dose Modifications

# Haematological toxicity

Table. Olaparib haematological toxicity management guidelines

Toxicity	Action
Any Grade 3	First occurrence
haematological toxicity	
 
Withhold dose for up to 28 days until recovery to Grade ≤1 then resume olaparib at the same dose level.
 
If symptoms do not recover to Grade ≤1 within 28 days, discontinue olaparib.
 
Second occurrence
 

	
 
Withhold dose for up to 28 days until recovery to Grade ≤1 then reduce olaparib to the first dose reduction level for haematological toxicity.
 
If symptoms do not recover to Grade ≤1 within 28 days, discontinue olaparib.
 
Third occurrence
 

	
 
Withhold dose for up to 28 days until recovery to Grade ≤1 then reduce olaparib to the second dose reduction level for haematological toxicity.
 
If symptoms do not recover to Grade ≤1 within 28 days, discontinue olaparib.
 
Fourth occurrence
 

	Discontinue olaparib.
Any Grade 4	First occurrence
haematological toxicity	
 
Withhold dose for up to 28 days until recovery to Grade ≤1 then reduce olaparib to the first dose reduction level for haematological toxicity.
 
If symptoms do not recover to Grade ≤1 within 28 days, discontinue olaparib
 
Second occurrence
 

	
 
Withhold dose for up to 28 days until recovery to Grade ≤1 then reduce olaparib to the second dose reduction level for haematological toxicity.
 
If symptoms do not recover to Grade ≤1 within 28 days, discontinue olaparib Third occurrence
 

	Discontinue olaparib
Anaemia	
 
Common treatable causes of anaemia (e.g. iron, vitamin B12 or folate deficiencies and hypothyroidism) should be investigated and appropriately managed. In some cases management of anaemia may require blood transfusions. The use of erythropoietin is not allowed at any stage.
 

IRAS Project Number: 249774

Toxicity	Action
Haemoglobin (Hb) <10g/dL	General management
but ≥8g/dL	Give appropriate supportive treatment and investigate causality.
(Grade 2)	
 
Investigator judgement to continue trial treatment with supportive
 

	treatment (e.g. transfusion) or interrupt dose for a maximum of 28 days, for
	investigations and supportive treatment.
	Before initiation of any treatment cycle (Day 1) the Hb must be >8g/dL
	(80g/L) (with the exception of Cycle 1, where Hb must be >10g/dL (100g/L)).
	First occurrence
	
 
General management as above, and resume olaparib at the same dose level.
 

	Subsequent occurrences
	• If Hb <10g/dL but ≥9g/dL: General management as above. Upon recovery
	dose reduction may be considered to reduce olaparib to the first dose
	reduction level for haematological toxicity as a first step and to second dose
	reduction as a second step.
	If Hb <9g/dL but ≥8g/dL: Interrupt dose for a maximum of 28 days until Hb
	≥9g/dL and upon recovery dose reduction may be considered to reduce
	olaparib to the first dose reduction level for haematological toxicity as a first
111- 40-7-11	step and to second dose reduction as a second step.
Hb <8g/dL	General management
(Grade ≥3)	Appropriate supportive treatment should be given (e.g. transfusion) and     acceptive investigated.
	causality investigated.
	• Interrupt olaparib for a maximum of 28 days until Hb≥8g/dL (i.e., Grade
	≤2).
	First occurrence
	
 
General management as above, and reduce olaparib to the first dose reduction level for haematological toxicity.
 

	Second occurrence
	General management as above, and reduce olaparib to the second dose
	reduction level for haematological toxicity.
	Third occurrence
	Discontinue olaparib.
Neutropenia, leukopenia	Neutropenia, leukopenia and thrombocytopenia should be managed as
and thrombocytopenia	deemed appropriate by the Investigator with close follow up.
, .	
 
For toxicity of Grades 1-2, appropriate supportive treatment should be given
 

	and causality investigated. Trial treatment can be interrupted for a
	maximum of 28 days at the Investigator's discretion.
	If Grade ≥3 neutropenia occurs interrupt trial treatment and follow the
	instructions for any haematological toxicity above as appropriate.
	Primary prophylaxis with granulocyte colony-stimulating factor (G-CSF) is
	not recommended, however, if a patient develops febrile neutropenia, trial
	treatment should be interrupted for a maximum of 28 days and appropriate
	management including G-CSF should be given according to local hospital
	guidelines. Please note that G-CSF should not be used within at least 24
	hours (7 days for pegylated G-CSF) of the last dose of trial treatment unless
	absolutely necessary.
	Platelet transfusions, if indicated, should be done according to local hospital
	guidelines.

Toxicity	Action
Prolonged haematological toxicity such as ≥2 week interruption/delay in trial treatment due to Grade ≥3:  • Anaemia and/or development of blood transfusion dependence  • Neutropaenia (ANC <1 x 10°/L)  • Thrombocytopaenia and/or development of platelet transfusion dependence (platelet count <50 x 10°/L)	
 
Check weekly differential blood counts (including reticulocytes and peripheral blood smear).
 
If any blood parameters remain clinically abnormal after 28 days of dose interruption, the patient should be referred to a haematologist for further investigations. Bone marrow analysis and/or blood cytogenetic analysis should be considered at this stage according to standard local haematological practice. Bone marrow analysis should include an aspirate for cellular morphology, cytogenetic analysis and flow cytometry, and a core biopsy for bone marrow cellularity. If it is not possible to conduct cytogenetic analysis or flow cytometry on the bone marrow aspirate, then attempts should be made to carry out the tests on a blood sample. If findings are consistent with MDS/AML, trial treatment should be discontinued and a full description of findings should be submitted in an SAE report.
 
Trial treatment should be discontinued if blood counts do not recover to Grade ≤1 within 28 days of dose interruption.
 
Development of a confirmed MDS or other clonal blood disorder should be reported as an SAE, please refer to Section 16.
 
Trial treatment should be discontinued if the diagnosis of MDS and/or AML, or PRCA or AlHA is confirmed. Note: if PRCA or AlHA are observed in patients with germline BRCA1/2 mutation (cohort F), olaparib may be restarted outside of the protocol as part of standard of care treatment on haematological recovery according to investigator discretion.
 

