#### 25.1.2. Part 2 Discontinuation of Trial Treatment

Patients may discontinue olaparib and/or durvalumab early if they experience unacceptable toxicity or if the investigator believes further treatment with one or both IMPs is no longer appropriate or at the patient's request. Protocol-specified reasons for discontinuation include:

- Disease progression or recurrence
- Unacceptable toxicity
- Bone marrow findings consistent with myelodysplastic syndrome (MDS)/acute myeloid leukaemia (AML), pure red cell aplasia (PRCA) or auto-immune haemolytic anaemia (AIHA))
  - Note: if PRCA or AIHA are observed in patients with germline BRCA1/2 mutation (cohort F), olaparib may be restarted outside of the protocol as part of standard of care treatment on haematological recovery according to investigator discretion.
- Pregnancy
- Withdrawal of consent
- Serious non-attendance and/or persistent non-compliance with procedures defined in the trial protocol

Patients can continue on monotherapy trial treatment if one IMP is discontinued. All patients who discontinue both olaparib and durvalumab should continue to be followed up. Patients should be asked for consent for future linkage with routinely collected health data (via national registries) to trace their eventual vital status and assess subsequent unexpected co-morbidities.

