# Non-haematological toxicity

Table. Olaparib non-haematological toxicity management guidelines

Table. Olaparib non-haematological toxicity management guidelines		
Toxicity	Action	
Any non-haematological	First occurrence	
toxicity Grade ≥3	
 
Withhold dose for up to 28 days until recovery to Grade ≤1. For Grade 3 toxicity olaparib may be resumed at the same dose level at the discretion of the Investigator. In the case of Grade 4 toxicity olaparib should be reduced to the first dose reduction level for non-haematological toxicity.
 
If symptoms do not recover to Grade ≤1 (or recover to baseline level if baseline was Grade 2) within 28 days, discontinue olaparib. Patients with alopecia may continue on trial treatment.
 
Second occurrence
 
Withhold dose for up to 28 days until recovery to Grade ≤1 then reduce olaparib to the next dose reduction level for non-haematological toxicity.
 
If symptoms do not recover to Grade ≤1 (or recover to baseline level if baseline was Grade 2) within 28 days, discontinue olaparib. Patients with alopecia may continue on therapy.
 
Third occurrence
 
Withhold dose for up to 28 days until recovery to Grade ≤1 then reduce olaparib to the second dose reduction level for non-haematological toxicity. Patients who are currently receiving the second dose reduction level should discontinue olaparib.
 
	

Toxicity	Action	
	
 
If symptoms do not recover to Grade ≤1 (or recover to baseline level if baseline was Grade 2) within 28 days, discontinue olaparib. Patients with alopecia may continue on therapy.
 
Fourth occurrence
 
	
	Discontinue olaparib.	
New or worsening pulmonary symptoms  NB. Pneumonitis is an	If new or worsening pulmonary symptoms (e.g. dyspnoea) or radiological abnormalities occur in the absence of a clear diagnosis, an interruption in trial treatment dosing is recommended and further diagnostic workup (including a high resolution CT scan) should be performed to exclude pneumonitis.	

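### The Part 2 olaparib rows for Grade 3 and Grade 4 haematological toxicity name fixed dose levels regardless of current dose, so an already-reduced patient can be pointed to the same dose or to a barred higher one.

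*Protocol*

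**What the plan says.** Section 25.2.2 of the protocol sets the olaparib ladder for Part 2: 300 mg BD at the start, 250 mg BD as first reduction (the same for haematological and non-haematological toxicity), 200 mg BD as second reduction, and discontinuation as the third. It adds: "Once a reduction is made the patient should not increase back to a higher dose level".

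The haematological table in Section 25.2.3 has one row for any Grade 3 event and one for any Grade 4 event. At the second Grade 3 and the first Grade 4 occurrence the dose is withheld for up to 28 days until recovery, "then reduce olaparib to the first dose reduction level for haematological toxicity". At the third Grade 3 and the second Grade 4 occurrence the named level is the second one, 200 mg BD. The next occurrence in each row is a stop. Neither row mentions the current dose.

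The row for Hb below 8 g/dL is built the same way; its first occurrence reads "General management as above, and reduce olaparib to the first dose reduction level for haematological toxicity".

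Other olaparib rules in the same section can lower the dose first:
- Non-haematological table, first occurrence: "In the case of Grade 4 toxicity olaparib should be reduced to the first dose reduction level for non-haematological toxicity".
- Hepatic table: a Grade 3 ALT/AST or bilirubin event moves the patient to the next level down.
- Renal row: 200 mg BD is recommended for creatinine clearance of 31 to 50 ml/min, with the choice between a dose change and stopping left to the investigator.

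In the non-haematological table the second occurrence is a step to the next level, and the third adds a check on the current dose: "Patients who are currently receiving the second dose reduction level should discontinue olaparib".

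**The concern.** A rule that names an absolute dose works only if the patient arrives at it on the dose the author had in mind. Here that is 300 mg BD, or 250 mg BD for the later step. Part 2 olaparib is continuous for up to 13 cycles and several tables can each lower the dose, so a patient may meet a haematological row already reduced under another.

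At stake is the restart dose after a serious cytopenia. If the row names the dose on which a Grade 4 event has just occurred, a site that follows it restarts at that dose. If it names a higher dose that another section forbids, the site must work out the step for itself. Two sites could restart similar patients at different doses and both point to the protocol.

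**Working it through.** The plan states no figure to reproduce. The check sets each named dose beside each dose a patient could be on.

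**Inputs.** Possible current doses d: 300, 250, 200 mg BD (Section 25.2.2). Named doses N: 250 for the second Grade 3 and first Grade 4 steps; 200 for the third Grade 3 and second Grade 4 steps (Section 25.2.3).

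**Change at each step, N − d (mg BD):**

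| Current dose | Second Grade 3 or first Grade 4 (N = 250) | Third Grade 3 or second Grade 4 (N = 200) |
|---|---|---|
| 300 | 250 − 300 = −50, a reduction | not reached: an earlier step in the same row has already lowered the dose |
| 250 | 250 − 250 = 0, same dose | 200 − 250 = −50, a reduction |
| 200 | 250 − 200 = +50, barred by 25.2.2 | 200 − 200 = 0, no stop stated |

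**Can a patient be at 250 or 200 mg BD before any haematological event?** Yes:
- Grade 4 non-haematological event: 300 → 250.
- Grade 3 ALT/AST or bilirubin event: next level, so 300 → 250.
- A second non-haematological event of Grade 3 or higher after the first of these: next level, so 250 → 200.
- Moderate renal impairment, if the investigator follows the recommendation: 200.

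None of these is a haematological occurrence. A later Grade 4 cytopenia is therefore a first occurrence however Grade 3 and Grade 4 are counted.

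**Resulting paths:**
1. Grade 4 non-haematological or Grade 3 liver-test event (dose 250), then first Grade 4 cytopenia: named 250, change 0. With a dose-relative step: 200.
2. Patient at 200, then first Grade 4 cytopenia: named 250, barred, stay or stop not stated. With a dose-relative step: stop.

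**Purely haematological paths depend on how occurrences are counted, which the text does not say:**

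| Sequence | Counted per row | One shared count |
|---|---|---|
| Hb below 8 g/dL (dose 250), then Grade 4 neutropenia | first Grade 4 step, named 250: change 0 | second occurrence, named 200: a proper step-down |
| Grade 3, Grade 3, Grade 4 | 300, 250, then 250: change 0 | third occurrence in the Grade 4 row: stop |

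**Effect of a dose-relative rule on single-grade paths from 300 mg BD:** none. Grade 3 four times still gives 300, 250, 200, stop; Grade 4 three times still gives 250, 200, stop.

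**The case against.** The strongest reply is that Section 25.2.2 already supplies the answer. Its ladder is sequential, a third reduction means stopping, and no return to a higher level is allowed. Moving from 250 to 250 is not a reduction. Read together, the two sections would send a patient at 250 to 200 and stop a patient at 200. As evidence of intent this stands. But the bar on re-escalation does not exclude restarting at 250 from 250, and the row names that level. Later steps in the non-haematological table and the hepatic table use next-level or current-dose wording, so the authors knew how to direct this and did not do so here.

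A second reply is discretion and oversight. Neutropenia, leukopenia and thrombocytopenia are managed as "deemed appropriate by the Investigator with close follow up", Grade 3 or worse neutropenia follows the "instructions for any haematological toxicity above as appropriate", and either drug may be stopped early "if the investigator believes further treatment with one or both IMPs is no longer appropriate" (Section 25.1.2). Every Grade 4 event is a serious adverse event, and dosing is held until Grade 1 or lower with a 28-day limit. All of this limits harm. It permits a step-down or a stop without directing either, and the hold governs when dosing resumes, not at what dose. The rule in Section 25.1 to apply the more conservative modification covers overlap between olaparib and durvalumab guidelines, not between two olaparib rows.

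Third, the affected patients need compound events, and Part 2 entry requires creatinine clearance of at least 51 mL/min. This is fair and limits the size of the point.

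Fourth, requiring a stop at 200 mg BD goes beyond tidying words for a patient who is there only for renal function, and in Cohort F it would end trial olaparib in a population where the protocol regards benefit as established. This stands, and the fix allows for it.

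**Conclusion.** The point holds for patients already reduced under a non-haematological, hepatic or renal rule. At 250 mg BD a first Grade 4 cytopenia brings a named change of zero; at 200 mg BD it brings a target 50 mg BD above the current dose that another section forbids. These results need no assumption about how occurrences are counted. The route to 200 mg BD through the renal row does assume that the investigator follows a recommendation.

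A reader might infer more, and three such readings are not supported:
- That the protocol orders re-escalation. Section 25.2.2 bars it, so the fault is a conflict and a missing direction.
- That haematological events alone produce the fault. That is so only if occurrences are counted per row.
- That trial results are at risk. The Part 1 primary endpoints do not depend on Part 2 dosing.

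The scope is Part 2 safety in at most 23 treated patients (Section 5.1). The documents give no basis for a frequency and none is claimed. The rows should be corrected at the next amendment.

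**What to change.** In Section 25.2.3, keep the first Grade 3 haematological occurrence at the same dose. For later Grade 3 and all Grade 4 haematological occurrences, write: *reduce to the next dose level below the current dose; discontinue if already at the second reduction level (200 mg BD)*. Use the same wording in the row for Hb below 8 g/dL and for the first Grade 4 step of the non-haematological table, which also name fixed levels.

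State whether Grade 3 and Grade 4 haematological occurrences share one count. With dose-relative steps, this would matter mainly for whether a first Grade 3 event after a Grade 4 event keeps the same dose.

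For a patient at 200 mg BD solely because of renal impairment, the sponsor should confirm that stopping after a haematological event is the intended action, since that is a clinical decision.

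The cost is a change to a few table rows, with no extra visits or patients. The downside is that some already-reduced patients would step down or stop trial olaparib sooner than if a site restarted them at the named level.

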  - b. Systemic corticosteroids at physiologic doses not to exceed 10 mg/day of prednisone or its equivalent
  - c. Steroids as premedication for hypersensitivity reactions (e.g., CT scan premedication)
- 8. Receipt of live attenuated vaccine within 30 days prior to the first dose of durvalumab. Note: Patients who commence durvalumab therapy in Part 2 should not receive live vaccine whilst receiving durvalumab and up to 90 days after the last dose of durvalumab.
- 9. Known allergy or hypersensitivity to durvalumab or any excipient.

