# 25.3.4. Part 2 Durvalumab: Dose interruptions

As directed in Section 25.3.3 and the **Dosing Modification and Toxicity Management Guidelines** at Appendix 7, durvalumab treatment should be interrupted if patients experience any Grade ≥2 toxicity.

Following an interruption for Grade ≥2 toxicity, trial treatment may be delayed for up to 12 weeks until these toxicities have resolved to Grade ≤1 or returned to baseline.

Repeat dose interruptions are allowed as required, for a maximum of 12 weeks on each occasion. If a patient remains off trial treatment for >12 weeks, trial treatment should be permanently discontinued.

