EGFR Tyrosine Kinase Inhibitors (TKIs) should not be given concomitantly and should be used with caution in the 90 day period post the last dose of durvalumab. Increased incidences of pneumonitis (with third generation EGFR TKIs) and increased incidence of transaminase increases (with 1st generation EGFR TKIs) has been reported when durvalumab has been given concomitantly.

Live virus and live bacterial vaccines should not be administered whilst the patient is receiving trial treatment and during a period of 30 days following the last dose of trial treatment..

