			assessment of early morning adrenocorticotropin hormone (ACTH), cortisol, TSH and free T4; also consider gonadotropins, sex hormones, and prolactin levels, as well as cosyntropinstimulation test (though it may not be useful in diagnosing early secondary adrenal insufficiency).  - If TSH < 0.5 × LLN, or TSH >2 × ULN, or consistently out of range in 2 subsequent measurements, include free T4 at subsequent cycles as clinically indicated and consider consultation of an endocrinologist.
	Grade 2, 3, or 4	- For Grade 2-4 endocrinopathies other	For Grade 2, 3, or 4
		than hypothyroidism and type 1 diabetes mellitus (T1DM), consider holding study drug/study regimen	
 
Consult endocrinologist to guide evaluation of endocrine function and, as indicated by suspected endocrinopathy and as clinically indicated, consider pituitary scan.
 

		dose until acute symptoms resolve.  - Study drug/study regimen can be resumed once patient stabilizes and after completion of steroid taper (<10 mg prednisone, or equivalent).  - Patients with endocrinopathies who	
 
For all patients with abnormal endocrine work up, except those with isolated hypothyroidism or T1DM, and as guided by an endocrinologist, consider short-term corticosteroids (e.g., 1 to 2 mg/kg/day methylprednisolone or IV equivalent) and prompt initiation of treatment with relevant hormone replacement.
 

		may require prolonged or continued steroid replacement (e.g., adrenal	
 
Isolated hypothyroidism may be treated with replacement therapy, without study drug/study regimen interruption, and without corticosteroids.
 

		insufficiency) can be retreated with study drug/study regimen if the patient is clinically stable as per investigator or treating physician's	
 
Isolated T1DM may be treated with appropriate diabetic therapy, and without corticosteroids. Only hold study drug/study regimen in setting of hyperglycemia when diagnostic workup is positive for diabetic ketoacidosis.
 

		clinical judgement.	
 
For patients with normal endocrine workup (laboratory assessment or magnetic resonance imaging (MRI) scans), repeat laboratory assessments/MRI as clinically indicated.
 

Amylase/Lipase increased	Any Grade	General Guidance	For Any Grade
	(Refer to NCI CTCAE		
 
Patients should be thoroughly evaluated to rule out any alternative etiology (e.g. disease progression,
 

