	Grade 2, 3 or 4	
 
If Grade 2-4, permanently discontinue study drug/study regimen.
 
	For Grade 2-4  Monitor symptoms daily, hospitalize.  Consider cardiology consultation and a prompt start of high-dose/pulse corticosteroid therapy  Supportive care (e.g., oxygen).  If no improvement consider additional immunosuppressive therapy such as TNF inhibitors (e.g., infliximab), IVIG or plasmapheresis or other therapies depending on the clinical condition of the patient, based on the discretion of the treating specialist consultant ror relevant practice guidelines.  Caution: It is important to rule out sepsis and refer to infliximab label for general guidance before using infliximab. Infliximab is contraindicated for patients who have heart failure.
Myositis/ Polymyositis	Any Grade (Refer to NCI CTCAE applicable version in study protocol for	General Guidance	For Any Grade  - Patients should be thoroughly evaluated to rule out any alternative etiology (e.g., disease progression, other medications, or infections).

	Manitan national for since and the first
defining the CTCAE grade/severity)	
 
Monitor patients for signs and symptoms of poly/myositis. Typically, muscle weakness/pain occurs in proximal muscles including upper arms, thighs, shoulders, hips, neck and back, and; also difficulty breathing and/or trouble swallowing can occur and progress rapidly. Increased general feelings of tiredness and fatigue may occur, and there can be new-onset falling, difficulty getting up from a fall, and trouble climbing stairs, standing up from a seated position, and/or reaching up.
 

	
 
If poly/myositis is suspected, a Neurology consultation should be obtained early, with prompt guidance on diagnostic procedures. Myocarditis may co-occur with poly/myositis; refer to guidance under Myocarditis. Given breathing complications, refer to guidance under Pneumonitis/ILD. Given possibility of an existent (but previously unknown) autoimmune disorder, consider Rheumatology consultation.
 

	
 
Consider, as necessary, discussing with the Clinical Study Lead.
 

	
 
Consider that patients may present with or progress to rhabdomyolysis. Treat signs and symptoms as per institutional protocol or local clinical practice.
 

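### Part 2 olaparib rules for haemoglobin below 8 g/dL contradict each other on when to restart and when to stop for good

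*Protocol*

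**What the plan says.** **Olaparib, Protocol 25.2.3, haematological toxicity table.**
- The row for Hb below 8 g/dL, labelled Grade 3 or worse, says "Interrupt olaparib for a maximum of 28 days until Hb≥8g/dL" and glosses that level as Grade 2 or better. The first event leads to the first reduction level, the second to the second level, and the third to discontinuation.
- The row for any Grade 3 haematological toxicity says, for a first occurrence, "Withhold dose for up to 28 days until recovery to Grade ≤1 then resume olaparib at the same dose level". If Grade 1 is not reached in 28 days, olaparib stops.
- The row for prolonged haematological toxicity gives as its example an interruption of two weeks or more, and names Grade 3 or worse anaemia. It says "Trial treatment should be discontinued if blood counts do not recover to Grade ≤1 within 28 days of dose interruption".

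**Olaparib, Protocol 25.2.4.** In addition to the table, any Grade 3 or worse toxicity is held until Grade 1 or baseline. More than 28 days off drug means permanent discontinuation.

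**Durvalumab.** Section 25.3.4 states, as directed in 25.3.3 and Appendix 7, that "durvalumab treatment should be interrupted if patients experience any Grade ≥2 toxicity", with a delay of up to 12 weeks. Appendix 7 says of one endocrine event "Isolated hypothyroidism may be treated with replacement therapy, without study drug/study regimen interruption", and of myocarditis "If Grade 2-4, permanently discontinue study drug/study regimen".

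**Live vaccines.** Section 12.1.2 says patients "should not receive live vaccine whilst receiving durvalumab and up to 90 days after the last dose of durvalumab". Section 25.3.8 sets the ban while on treatment and "during a period of 30 days following the last dose of trial treatment".

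**The concern.** A restart rule and a stopping rule for the same adverse event have to agree, because a site cannot do both. Here the olaparib text gives two recovery thresholds for Hb below 8 g/dL, and the higher one carries mandatory discontinuation. A patient who recovers past one threshold but not the other can be managed in contradictory ways by two sites that each follow the protocol.

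At stake are the safety conduct of a 12-month treatment period and the meaning of the Part 2 discontinuation and exposure data. Some discontinuations would reflect which row a site read rather than what happened to the patient. The durvalumab and vaccine passages raise a milder form of the same problem: the body text and the passage it relies on, or parallels, do not match.

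**Working it through.** No sample size, power or error rate is involved, so the check sets the rules side by side.

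**Step 1. Translate grades into haemoglobin.** The anaemia row in 25.2.3 defines Grade 2 as Hb below 10 and at least 8 g/dL. Grade 1 or better is therefore Hb of at least 10 g/dL, and Grade 2 or better is Hb of at least 8 g/dL.

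**Step 2. Check the baseline alternative in 25.2.4.** Part 2 entry requires Hb of at least 10 g/dL (12.1.1), and Cycle 1 requires more than 10 g/dL (25.2.2). Baseline is never Grade 2, so this alternative cannot lower the threshold below 10 g/dL.

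**Step 3. Compare the rules for one episode of Hb below 8 g/dL.**

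| Rule | Recovery needed | If not met | Action by occurrence |
|---|---|---|---|
| 25.2.3, Hb <8 row | Hb ≥8 | 28-day maximum hold | 1st: first reduction; 2nd: second reduction; 3rd: stop |
| 25.2.3, any Grade 3 | Hb ≥10 | stop at 28 days | 1st: same dose; 2nd: first reduction; 3rd: second reduction; 4th: stop |
| 25.2.3, prolonged | Hb ≥10 | stop at 28 days | not given |
| 25.2.4 | Hb ≥10 | stop after 28 days off | not given |

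The any Grade 4 row has the same occurrence ladder as the Hb <8 row, but it too requires Grade 1.

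**Step 4. Run cases through the table.**
- Day 10, Hb 8.5 g/dL: the Hb <8 row restarts at a reduced level. Section 25.2.4 keeps the patient off drug. The prolonged row's two-week example is not met.
- Day 28, still off drug, Hb 8.5 g/dL: the Hb <8 row restarts. The prolonged row discontinues. Section 25.2.4 does not allow a restart at this level and stops olaparib once 28 days are exceeded.
- Day 28, Hb 10 g/dL or more: all rules allow a restart. For a first Grade 3 event the dose is reduced under the Hb <8 row and unchanged under the general row, if the general row applies.
- Day 28, Hb still below 8 g/dL: no rule allows a restart.

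The zone of conflict is 8 ≤ Hb < 10 g/dL, the whole of the protocol's Grade 2 band.

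**Step 5. Look for a tie-break.** Section 25.1 tells sites to take the more conservative action when the olaparib and durvalumab guidelines both apply. It does not choose between two rules for the same drug. The protocol does not say whether the Hb <8 row replaces the general Grade 3 row.

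**Step 6. Durvalumab.** Section 25.3.4 interrupts for every Grade 2 or worse toxicity and cites Appendix 7 for this. Appendix 7 does not require a hold for isolated hypothyroidism, for Grade 2 skin events lasting no more than one week, or for events not considered related to treatment. Section 25.3.4 also does not mention the events for which Appendix 7 requires permanent discontinuation, such as Grade 2 to 4 myocarditis and Grade 3 or 4 pneumonitis.

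**Step 7. Live vaccines.** Let D be the day of the last durvalumab dose and T the day of the last trial treatment. The windows end at D + 90 (12.1.2) and T + 30 (25.3.8). If D = T, they differ by 90 − 30 = 60 days. Section 25.1.2 allows one drug to continue alone. If olaparib continues for more than 60 days after durvalumab, T + 30 becomes the later date. The anchors differ as well as the lengths.

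**Step 8. Size.** Cohorts F and G have maxima of 8 and 15, so at most 8 + 15 = 23 patients can receive Part 2 trial treatment (section 5.1). At that maximum, one patient classified differently moves the discontinuation proportion by 1/23 = 4.3 percentage points. The protocol gives no expected frequency of Hb below 8 g/dL, so the number affected cannot be estimated.

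**The case against.** The best defence is that a specific row overrides a general one. The Hb <8 row has its own occurrence ladder. The neutropenia entry expressly sends sites back to the general haematological instructions, and the anaemia row does not. The cycle-start criterion in 25.2.2, Hb of at least 8 g/dL, fits the anaemia row. This weakens the dose conflict with the general Grade 3 row, which is better described as unstated precedence. It does not remove the main conflict: the prolonged row names anaemia itself, and 25.2.4 says that it applies in addition to the table. One limit stands. The prolonged row is aimed at interruptions of about two weeks or more, so a patient who reaches 8 g/dL sooner is caught by 25.2.4 and not by that row.

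A reader might infer that 25.3.4 contradicts Appendix 7 in both directions. The documents do not support that. Section 25.3.4 cites Appendix 7, and its 12 weeks is a permitted maximum that confers no right to resume. A site that permanently stops durvalumab for myocarditis or pneumonitis breaches neither text. Direct conflict remains only where Appendix 7 requires no hold. The deference is imperfectly signposted, since two pointers in 25.3.3 name an Appendix 9 that this version does not contain.

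A reader might also infer that the vaccine windows force opposite actions. They do not: a site that waits for the later end date complies with both.

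**Conclusion.** The contradiction in the olaparib rules for Hb below 8 g/dL is real and is in the current text. For a patient off drug at day 28 with Hb from 8 to below 10 g/dL, restart and discontinuation are each prescribed. This rests only on the protocol's own grade band and entry criteria. The durvalumab and vaccine items are lesser inconsistencies of wording and do not show opposite instructions for the same event.

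The reach is limited. Part 2 is described as exploratory and descriptive (17.1.2). The primary endpoints are read at the end of the preoperative window, and the adverse event endpoint is at one month after surgery. A reader might infer that the trial's activity conclusions are at risk, but nothing in the Part 1 two-stage designs depends on these passages. Nor would all 23 patients necessarily receive the combination, since those ineligible for durvalumab receive olaparib alone (12.1.3). What is affected is safety conduct, exposure, and the exploratory ctDNA descriptions in treated patients. Correction is still needed, because the passages govern permanent discontinuation.

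**What to change.** Reconcile the passages as follows; the sponsor's clinical team decides which rule applies in each case.
- **Olaparib:** give Hb below 8 g/dL one recovery threshold and one action per occurrence across the general, anaemia and prolonged-toxicity rows of 25.2.3 and section 25.2.4. State whether the anaemia row replaces the general row.
- **Durvalumab:** state in 25.3.4 that the event-specific rules of Appendix 7 govern, or make the two match.
- **Live vaccines:** state one window with one anchor date in 12.1.2 and 25.3.8.

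The cost is a wording amendment and a memo to sites. Sample size, endpoints and analyses do not change.
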